10.0 DATA SAFETY MONITORING AND ADVERSE EVENT (AE) MONITORING AND REPORTING

10.1 Data and Safety Monitoring / Quality Assurance Committee

This study will be governed by the UMGCC Data Safety Monitoring / Quality Assurance Committee (DSMQAC). The study will be sent to the DSMQAC for a mandatory interim review after the first 6 patients have been accrued. Once the DSMQAC has reviewed and approved the initial 6 patients on the study, 24 additional patients will be enrolled. The study will be reviewed by the DSMQAC on an annual basis and a report will be uploaded in the continuing review submitted to the Institutional Review Board (IRB).

On the basis of an optimal two-stage design to test the null hypothesis that $P \leq 0.05$ (poor pCR response rate) versus the alternative that $P > 0.25$ (UMGCC DSMQAC committee feels that 25% response rate is a reasonable threshold) has an expected sample size of 16.76 and a probability of early termination of 0.63. If preoperative concurrent LDFRT and FOLFOX is actually not effective, there is a 0.05 probability of concluding that it is. If the treatment combination is actually effective, there is a 0.10 probability of concluding that it is not. After treating 9 patients in the first stage, the study will be terminated if 0 respond. If the trial goes on to the second stage, a total of 30 patients will be studied. If the total number responding is less than or equal to 3, the treatment combination will be rejected.

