- Grade 3 or 4 myelosuppression and hospitalization resulting from such do not require expedited reporting via CICERO but will be reported in ONCORE and will be submitted as part of study results.
- Other grade 1-4 events that are expected do not require expedited reporting via CICERO, even if they result in hospitalization.
- Grade 4 events that are unexpected and that are at probably related (per UMB IRB definition) to treatment must be reported via CICERO within 5 calendar days per UMB IRB guidelines.
- All new malignancies should be reported to the IRB whether or not they are thought to be related to either previous or current treatment. All new malignancies should be reported, i.e., solid tumors (including non-melanoma skin malignancies), hematologic malignancies, myelodysplastic syndrome (MDS)/acute myelogenous leukemia (AML), and *insitu* tumors. In CTCAE version 4.0, the new malignancies (both second and secondary) may be reported as one of the following:
 - (1) Leukemia secondary to oncology chemotherapy,
 - (2) Myelodysplastic syndrome,
 - (3) Treatment-related secondary malignancy, or
 - (4) Neoplasm other, malignant (grade 3 or 4).Whenever possible, the IRB reports for new malignancies should include, tumor pathology, history of prior tumors, prior treatment/current treatment including duration, any associated risk factors or evidence regarding how long the new malignancy may have been present, when and how the new malignancy was detected, molecular characterization or cytogenetics of the original tumor (if available) and of any new tumor, and new malignancy treatment and outcome, if available.
- All pregnancies and suspected pregnancies occurring in female patients or in the partner of a male patient during therapy or within 28 days after completion of treatment on GCC 1314 must be reported to the IRB. In CTCAE version 4.0, use the event term, "*pregnancy, puerperium, and perinatal condition-other, fetal exposure (grade4)*".
- IRB reports should be amended upon completion of the pregnancy to report pregnancy outcome (e.g. normal, spontaneous abortion, therapeutic abortion, fetal death, congenital abnormalities).
- The IRB report should be amended for any neonatal deaths or complications occurring within 28 days of birth independent of attribution. Infant deaths occurring after 28 days considered to be related to in utero exposure to the agents used in this trial should be reported to the IRB.

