11.2 Chemotherapy

The patient will discontinue FOLFOX and be referred for treatment off protocol if the patient requires dose reduction beyond level -2 during cycles 1-5 of preoperative therapy or if FOLFOX is held due to toxicity for more than 30 days from the previous cycle.

The precise dose modification schema used and the symmetry of dose modification may be left to the discretion of the treatment physician.

Table 11.2 FOLFOX dose levels

Dose level*	5-FU infusion	5-FU bolus	Oxaliplatin
0	1200 mg/m ² /day x 2 days (2400 mg/m ² over 48 hours)	400 mg/m ²	85 mg/m ²
-1	960 mg/m ² /day x 2 days (1920 mg/m ² over 48 hours)	320 mg/m ²	65 mg/m ²
-2	800 mg/m ² /day x 2 days (1600 mg/m ² over 48 hours)	270 mg/m ²	50 mg/m ²
-3	680 mg/m ² /day x 2 days (1360 mg/m ² over 48 hours)	230 mg/m ²	40 mg/m ²

*Dose level 0 refers to the starting dose

Table 11.3 FOLFOX dose modifications based on adverse events

System/organ/class	Adverse event	Agent	Dosage change
Blood and lymphatic systemic disorders	Neutropenia grade ≥2 and/or Thrombocytopenia grade ≥ 2	5-FU Oxaliplatin	Hold up to 16 days until ANC ≥ 1200 K/mcL. If recovered in ≤ 16 days, then resume at next lower dose level. Hold up to 16 days until platelets ≥ 75,000 K/mcL. If recovered in ≤ 16 days, then resume at next lower dose level.
Gastrointestinal disorders	Nausea grade 2 Nausea grade 3	Oxaliplatin	Intensify antiemetic therapy and proceed with FOLFOX at current dose level. Maximal antiemetic therapy includes a 5-HT inhibitor in addition to Compazine, lorazepam, aprepitant, and dexamethasone If resolved to < grade 2 on day of treatment, may proceed with intensification of antiemetic therapy and current dose level of FOLFOX. If not resolved to < grade 2 on day of therapy, intensify antiemetic regimen

	Nausea grade 4	5-FU Oxaliplatin	and proceed with FOLFOX when resolved to < grade 2. May decrease oxaliplatin one dose level if not responsive to maximal antiemetic support.
Vomiting grade 2	If resolved to < grade 2 on day of treatment, may proceed with intensification of antiemetic therapy and current dose level of FOLFOX. If not resolved to < grade 2 on day of therapy, intensify antiemetic regimen and proceed with FOLFOX when resolved to < grade 2. Decrease oxaliplatin one dose level if not responsive to maximal antiemetic support.		

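### The only numeric early stopping rule counts pCR; the protocol states no toxicity criterion for the 6-patient review, the annual reviews or the accrual of patients 7 to 30

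*Combined protocol and SAP*

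**What the plan says.** Section 10.1 sets a two-stage design on pCR, with null rate 5% and alternative 25%. The early stop is "After treating 9 patients in the first stage, the study will be terminated if 0 respond". The second cut-off, 3 or fewer responders among 30, is a final decision and cannot stop accrual.

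The same section gives the DSMQAC a mandatory review once 6 patients have been accrued, and then: "Once the DSMQAC has reviewed and approved the initial 6 patients on the study, 24 additional patients will be enrolled". After that, "The study will be reviewed by the DSMQAC on an annual basis". Neither review has a stated toxicity criterion.

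The toxicity limits in the protocol act on one patient at a time. Section 11.2 takes a patient off FOLFOX for a reduction below level -2 in cycles 1 to 5, or "if FOLFOX is held due to toxicity for more than 30 days from the previous cycle". Section 12.0 lists a grade 3-4 event lasting 3 weeks or more among the reasons for discontinuing a patient. These events are not added up against a trial-level limit.

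On reporting, Section 10.3 sends all adverse events to ONCORE. It also requires a report to the IRB within 5 business days when a known risk becomes more frequent or more severe. Section 10.5 removes grade 3-4 myelosuppression from expedited IRB reporting and adds: "Other grade 1-4 events that are expected do not require expedited reporting via CICERO, even if they result in hospitalization".

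Toxicity is not an objective in Section 2.0, and Section 14.0 contains no safety analysis.

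**The concern.** Section 1.3 makes it a hypothesis that LDFRT can be added safely to full-dose FOLFOX, and expects no more severe toxicity than with FOLFOX alone. The clinical LDFRT experience described in 1.2.2 is with carboplatin/paclitaxel, gemcitabine and cisplatin. The only FOLFOX-agent data shown (1.2.1) are from cell lines. Safety of the combination is therefore still an open question when the trial starts, yet the one numeric rule that can end accrual responds only to lack of pCR.

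If the combination is active but causes more expected toxicity than is acceptable, detection depends on someone judging the accumulated events excessive without a stated reference rate. Those exposed meanwhile are the 24 patients treated after the 6-patient review.

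**Working it through.** **1. The plan's own design.** Inputs from 10.1: first stage 9, stop at 0; total 30, reject at 3 or fewer; pCR 5% versus 25%.
- Early termination at 5%: 0.95^9 = 0.630 (stated 0.63).
- Expected size at 5%: 9 + (1 - 0.630) x 21 = 16.76 (stated 16.76).
- Exact type I error 0.0489 and power 0.902, matching the stated 0.05 and 0.10 error rates.

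The pCR design is correctly computed and is not in dispute.

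**2. What that rule does with an active regimen.** P(continue) = 1 - (1 - p)^9:
- pCR 25% (the 10.1 alternative): 1 - 0.075 = 0.925
- pCR 27% (the pilot rate in 1.1.5): 1 - 0.059 = 0.941
- pCR 35% (the hypothesis in 14.0): 1 - 0.021 = 0.979

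Toxicity does not enter the formula.

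**3. What the 6-patient review can see.** It is triggered by accrual. Treatment lasts 6 x 14 = 84 days, or 84/30.4 = 2.76 months. Accrual is 30/15 = 2.0 per month (10.2) or 30/24 = 1.25 per month (14.0). Suppose data are cut at the sixth registration, accrual is even and treatment starts at registration. The first patient has then been on study 5 x 0.5 = 2.5 months at the faster rate, so nobody has finished. At the slower rate the first two have been on study 5 x 0.8 = 4.0 and 4 x 0.8 = 3.2 months, so two have finished.

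Even with complete data, six patients are a weak screen. At an assumed true event rate of 40%, P(2 or fewer of 6) = 0.6^6 + 6 x 0.4 x 0.6^5 + 15 x 0.4^2 x 0.6^4 = 0.544.

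**4. Patients between the two scheduled reviews.** Counting the year from the opening of accrual, with no halt at the 6-patient review:
- 2.0 x 12 - 6 = 18
- 1.25 x 12 - 6 = 9

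**5. What a boundary would add (illustration).** The documents give no acceptable toxicity rate, so 10% and 15% are assumptions. The limit at each look is the smallest x with P(X >= x | n, p0) <= 0.05. Looks are at 6, 12, 18 and 24 patients who have finished or stopped treatment. Pause probabilities come from exact binomial recursion over the four looks.

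| Assumed acceptable rate | Limits at 6 / 12 / 18 / 24 | Pause probability at true rate |
|---|---|---|
| 10% | 3 / 4 / 5 / 6 | 0.06 at 10%; 0.64 at 25%; 0.81 at 30%; 0.97 at 40% |
| 15% | 3 / 5 / 6 / 8 | 0.08 at 15%; 0.58 at 30%; 0.87 at 40% |

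**6. Enrolment at the pause.** Registration continues while patients are treated, so each look comes after a further 2.0 x 2.76 = 5.5 or 1.25 x 2.76 = 3.45 registrations. For the 10% limits at a true 30%, the first-crossing probabilities at the four looks are 0.256, 0.274, 0.174 and 0.107 (sum 0.811). Counting 30 when there is no pause, at 2.0 per month:

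0.256 x 11.5 + 0.274 x 17.5 + 0.174 x 23.5 + 0.107 x 29.5 + 0.189 x 30 = 20.7

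At 1.25 per month it is 19.0. At a true 40% the two figures are 16.6 and 14.6.

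**The case against.** The strongest reply is that the trial does have safety oversight. The DSMQAC governs the study, patients 7 to 30 depend on its approval, and it reviews annually. The IRB route in 10.3 covers a more frequent known risk, and the definition of an unexpected harm there refers to frequency, so an excess of a listed toxicity can become reportable. The Section 10.5 exemption concerns expedited IRB reports only; every event still goes to ONCORE.

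All of this stands, and it rules out three stronger readings that a reader might infer:
- *The pCR rule is the only thing that can stop the trial.* The approval after 6 patients can also stop it.
- *A toxic but active regimen must run to 30.* The 0.925 to 0.979 describes the pCR rule alone and says nothing about what the committee or IRB would do.
- *Excess toxicity triggers nothing between annual reviews.* The IRB reporting duty applies throughout.

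Section 10.3 also points to a DSMQAC document that is not available here. Committee procedures may contain triggers, so the finding is about the protocol text.

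Other limits also stand. The unacceptable toxicity described in 1.2 concerns standard pelvic RT at 5040 cGy, not 960 cGy, and 1.2.2 reports no added toxicity from LDFRT in the gemcitabine trial. It is tempting to use the pilot's 2 non-completers among 32 as a reference rate, but 1.1.5 attributes both to probable bevacizumab effects, and that drug is not given here. Setting enrolment equal to the look number would give 16.2 at a true 30% and 11.2 at 40%, but this requires suspending registration at every look. Finally, dose modification is discretionary (5.1.2, 11.2), so some candidate events partly reflect physician practice.

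What the reply leaves unanswered is that each of these routes rests on judgment without a stated count or reference rate.

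**Conclusion.** The point holds in this form. The protocol has one numeric early stop, on pCR, and it is blind to toxicity. Judgment-based oversight exists, but the protocol gives it no toxicity criterion, and no boundary covers patients 7 to 30. The first review may see few or no completed treatments, and the next scheduled one comes 9 to 18 patients later.

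The pCR figures are exact. The 9 to 18 rests on even accrual over 24 or 15 months. The pause probabilities rest on assumed acceptable rates, independent events and the four looks shown. They illustrate what a boundary can do and do not establish that 10% or 15% is the right rate. The saving is real but moderate: under the 10% limits, expected enrolment at the pause is about 19 to 21 at a true 30% and 15 to 17 at 40%, against a planned 30. This is an inexpensive improvement in patient protection. It does not invalidate the pCR design.

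**What to change.** Add to 10.1 a trial-level toxicity boundary that runs beside the pCR rule. Registration pauses for DSMQAC review when the cumulative number of patients with a counted toxicity event reaches an exact binomial limit. The check is made at stated numbers of patients who have finished or stopped treatment, for example 6, 12, 18 and 24. Print the limits, the pause probabilities over a range of true rates, and the expected enrolment allowing for registrations during treatment.

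The investigator and the DSMQAC choose which of the events already recorded in ONCORE count, and what rate is acceptable. The definitions should be tight enough for two readers to reach the same count. The boundary triggers a review only; no patient-level dose, hold or discontinuation rule changes.

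The cost is an amendment of one paragraph and a small table, using the existing committee and data, with no extra patients or visits. The downside is roughly a 6% to 8% chance of an unnecessary pause when the true rate equals the acceptable rate (0.06 and 0.08 in the two illustrations), and a short delay whenever a pause occurs.

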2.0 OBJECTIVES

2.1 Primary Objective

To determine whether the addition of concurrent LDFRT to neoadjuvant full dose FOLFOX results in a pCR response rate of at least 35%.

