8.2 Degree of pathologic treatment response

8.2.1 Pathological complete response (pCR)

A pCR indicates that no gross or microscopic tumor is identified anywhere within the primary tumor specimen or any lymph nodes.

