14.0 STATISTICS

Our hypothesis is that preoperative concurrent LDFRT and FOLFOX will result in a pCR rate of at least 35%. Thus our power analysis will rely on precision related to estimating the CR rate. Additionally, given that we will use the information from this study to design a prospective experimental study, we seek to enroll 30 patients within 24 months. As such, a sample size of 30 patients produces a two-sided 95% confidence interval with a width equal to 0.36 when the CR rate is 35%.

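### The primary objective (pCR of at least 35%) has no decision criterion, and the only efficacy rule, 5% versus 25% in Section 10.1, can be read as calling 4/30 effective

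*Combined protocol and SAP*

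**What the plan says.** Section 2.1 sets out to determine whether the combination "results in a pCR response rate of at least 35" percent. Section 14.0 repeats 35% as the hypothesis and sizes the trial by precision: "Thus our power analysis will rely on precision related to estimating the CR rate", and "a sample size of 30 patients produces a two-sided 95% confidence interval with a width equal to 0.36 when the CR rate is 35" percent. Section 1.3 adds a second target, a significant increase over the 27% pCR of the pilot described in Section 1.1.5. Section 14.0 also states the intended use: "given that we will use the information from this study to design a prospective experimental study".

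The only trial-level efficacy rule is in Section 10.1, on data and safety monitoring. It is an optimal two-stage design with null P ≤ 0.05 and alternative P > 0.25. The 25% is attributed to the monitoring committee: "UMGCC DSMQAC committee feels that 25% response rate is a reasonable threshold". The trial stops if none of the first 9 patients responds. At 30 patients, "If the total number responding is less than or equal to 3, the treatment combination will be rejected". The type I error is described this way: "If preoperative concurrent LDFRT and FOLFOX is actually not effective, there is a 0.05 probability of concluding that it is".

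Section 8.2.1 defines pCR as a finding that "no gross or microscopic tumor is identified anywhere within the primary tumor specimen or any lymph nodes". Sections 5.1.3 and 6.2.1.3 send some patients to standard chemoradiation before surgery, which 6.2.1.3 describes as off protocol.

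**The concern.** The objective is a yes/no question about 35%, but no section gives a responder count, a null rate, or a rule on the estimate or a confidence bound for answering it. The one rule that exists concerns other rates. By its own error-rate sentence, the opposite of rejection is a conclusion that the treatment is effective. Nothing links 5% and 25% to 27% or 35%.

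Two things are at stake. First, a result of 4 or 5 pCRs in 30 could be reported as effective under 10.1 while its own confidence interval excludes the target. For any other result, the answer depends on a criterion chosen after the data are seen. The results are meant to inform the design of a further study. Second, the plan does not say how patients without TME are counted, and it does not exclude from pCR a specimen taken after off-protocol chemoradiation. The regimen could be credited with a response to another treatment.

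**Working it through.** **Inputs.** From 10.1: p0 = 0.05, p1 = 0.25, stop at 0/9, reject at ≤ 3/30. From 2.1 and 14.0: 35%, N = 30. Reference pCR rates quoted in Section 1.1 and its subsections, all from other regimens: 8%, 15% and 27% (8/30). All figures assume 30 patients in the denominator if the trial is not stopped at stage 1.

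**Reproducing 10.1.** Early termination at p is (1 − p)^9; at 5%, 0.95^9 = 0.630. Expected N = 9 + 21 × (1 − 0.630) = 16.76. The probability of passing is the sum over x = 1 to 9 of b(x; 9, p) × P(Y ≥ max(0, 4 − x)), with Y ~ Binomial(21, p). This gives 0.0489 at 5% and 0.902 at 25%. All stated figures hold, and a search confirms that 0/9 and 3/30 is the optimal design for these inputs.

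**Reproducing 14.0.** The exact (Clopper-Pearson) interval at 0.35 × 30 = 10.5 responders is 0.186 to 0.545, width 0.359, which matches 0.36.

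**What the rule does at other true rates** (stage 1 stop included):

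| True pCR | P(pass 10.1) | P(4 or 5 pCRs) |
|---|---|---|
| 8% | 0.18 | 0.15 |
| 15% | 0.59 | 0.32 |
| 27% | 0.93 | 0.10 |
| 35% | 0.98 | 0.02 |

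**Exact 95% intervals**, with lower limit the 0.025 quantile of Beta(x, n − x + 1) and upper limit the 0.975 quantile of Beta(x + 1, n − x):

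| Result | Interval |
|---|---|
| 3/30 | 2.1% to 26.5% |
| 4/30 | 3.8% to 30.7% |
| 5/30 | 5.6% to 34.7% |
| 6/30 | 7.7% to 38.6% |
| 16/30 | 34.3% to 71.7% |
| 17/30 | 37.4% to 74.5% |

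So 4/30 and 5/30 are the two results that pass 10.1 while the interval excludes 35%. These are ordinary exact intervals, not adjusted for the 0/9 stop, which has probability 0.65^9 = 0.021 at a true 35%.

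**Three possible readings of the objective, at a true pCR of 35%:**
- passing 10.1 (≥ 4/30): probability 0.98
- point estimate at least 35% (≥ 11/30, since 10/30 = 33.3%): 0.49
- interval wholly above 35% (≥ 17/30): 0.01

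The answer therefore depends mainly on which reading is chosen.

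**The case against.** The best defence is that 10.1 is only a floor and 14.0 is pure estimation. The operative sentences of 10.1 only terminate or reject, the rule sits in the monitoring section, and 25% is the committee's threshold. Sizing by precision is legitimate, and a published 4/30 would carry its own interval. At a true 35%, 4 or 5 pCRs has probability only 0.02. Much of this stands. A reader might infer that the plan declares the 35% objective met at 4/30; no section says that. What remains is that the error-rate sentence equates passing with a conclusion of effectiveness, nothing limits that meaning, and an objective to determine whether pCR reaches 35% has no criterion for any result.

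A reader might also infer that the 0.05 and 0.10 error rates hold only at exactly 5% and 25%. They do not: the pass probability rises with P, so they are upper bounds over P ≤ 0.05 and P ≥ 0.25. They simply say nothing about 35%.

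Finally, a reader might infer from Section 8.2 that a patient without TME is neither pCR nor non-pCR. That over-reads it. The non-pCR definition in 8.2.2 is worded as inclusive rather than exhaustive, and 10.1 counts responders among treated patients, which suggests a treated-patient denominator. The narrower point stands: the handling of such patients is not stated, and specimens taken after off-protocol chemoradiation are not excluded.

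**Conclusion.** The concern holds and should be fixed. There is no arithmetic error in either section. The fault is that the only efficacy rule addresses 5% versus 25%, while the 35% objective and the hypothesised gain over 27% have no criterion. A regimen with a true pCR of 27%, no better than the pilot's rate, passes with probability 0.93, and one at 15% passes with 0.59. Passing is thus weak evidence about either target.

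A criterion alone would not rescue the objective as worded. At N = 30, results of 6 to 16 pCRs neither exclude 35% nor place the interval above it. That range has probability 0.95 at a true 35% and 0.83 at a true 27%. The design can estimate pCR; it cannot determine whether it is at least 35%.

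The figures rest on 30 patients in the denominator and unadjusted exact intervals. The count of two conflicting results depends on the interval reading; on a point-estimate reading the conflict runs from 4/30 to 10/30.

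**What to change.** N, the 0/9 and 3/30 cutoffs and accrual stay unchanged.

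1. **Section 10.1.** Label the rule a minimum-activity floor. For this rule only, define not effective as P ≤ 0.05 and effective as P ≥ 0.25. State that passing is not a conclusion that pCR is at least 35% or better than 27%.
2. **Section 14.0, analysis.** Make the primary analysis the pCR proportion with an exact two-sided 95% CI among all patients who start protocol treatment. Count patients without TME, or with off-protocol chemoradiation before TME, as non-pCR. Classify patients who stop protocol treatment early and go straight to TME by their specimen. Use the same classification for 0/9 and 3/30.
3. **Sections 2.1 and 14.0, objective and reading.** Reword the objective as estimating the pCR rate. For 30 patients, state in advance: 5 or fewer pCRs, inconsistent with 35%; 6 to 16, compatible with 35% but not shown to reach it; 17 or more, interval above 35%. Recompute the cut points if the number starting treatment is not 30. Report the estimate and interval descriptively beside the pilot's 27%.

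The cost is a wording amendment and a more modest claim. The rate may also be lower than a completers-only figure, which matters for the pilot comparison. The pilot's 27% is 8 of 30 completers, and the documents do not allow its two non-completers to be classified. The figure 8/32 = 25% applies only if both are assumed to be non-pCR.
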